29. Presence of intramural thrombus, tumor or other abnormality that precludes vascular access, or manipulation of the catheter.
30. Presence of an IVC filter
31. Presence of a condition that precludes vascular access.
32. Life expectancy or other disease processes likely to limit survival to less than 12 months.
33. Presenting contra-indication for the devices (e.g. TTE, CT, Holter, etc.) used in the study, as indicated in the respective instructions for use.
34. Categorized as a vulnerable population and requires special treatment with respect to safeguards of well-being

Additional exclusion criteria for Neurological Assessment Evaluable (NAE) subjects:

35. Contraindication to use of contrast agents for MRI such as advanced renal disease, etc. (at PI discretion)
36. Presence of iron-containing metal fragments in the body
37. Unresolved pre-existing neurological deficit.

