- **For subjects included in the neurological assessment subgroup, Cerebral MRI, Neurological Exam and Neurological Evaluation using the Montreal Cognitive Assessment (MoCA), NIH Stroke Scale and Modified Rankin Scale (mRS)** are required to be performed within 72- hours pre-procedure to evaluate the neurological condition and presence of neurological deficits of the subjects before undergoing study ablation procedure. A certified/qualified neurologist must perform neurologic exams at pre-and post-ablation and possibly at other follow-up visits, pending previous findings of micro-emboli/neurologic deficits. Pre-and post-ablation cerebral MRIs will be analyzed by a central core lab to determine the frequency, size, and anatomical location of cerebral micro-emboli, if any.
- Imaging for **detection of left atrial thrombus** or other structural contraindications to an ablation procedure is mandatory the day before or the day of the ablation procedure. Presence of a thrombus will require postponement of the ablation procedure or may even lead to exclusion of the subject from further study involvement. The imaging method to be used for atrial thrombus detection is transesophageal echocardiography (TEE) or intracardiac Echocardiography (ICE)

- **Pregnancy test** must be done on all women of childbearing age and potential, within 72 hours prior to the procedure and documented in the subject’s medical chart.
- **Quality Of Life questionnaire AFEQT** to be collected prior to procedure
- **Adverse Events** must be collected from the time the subject signs the informed consent onwards

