#### **8.2.4 Pre-Discharge Assessments**

Prior to hospital discharge, the following assessments should be performed:

- Cardiac and Anti-Coagulation Medication Regimen.
- TTE
- Adverse Events
- ECG in case standard of care
- For subjects in the neurological assessment subgroup: Cerebral MRI, Neurological exam and Neurological Evaluation using the NIH stroke Scale within 48- hours post procedure, prior to discharge. A certified/qualified neurologist must perform neurologic exams at pre-and post-ablation and possibly at other follow-up visits, pending previous findings of micro-emboli/neurologic deficits.

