#### **At 1, 3, 6 and, 12month follow-up visits, the following assessments will be performed:**

- Adverse events (1M through 12M)
  - Cardiac and Anti-coagulation medication regimen (1M through 12M)
  - Atypical (left side) AFL/AT/AF recurrences and repeat ablations (1M through 12M)
  - NYHA Functional Class Scale (3M)
  - 12 Lead-ECG (if completed per standard of care)
  - Quality of Life questionnaire AFEQT (3, 6 and 12M)
  - Cardiac CT/MRA (3M): 3M follow-up CT/MRA should be performed for subjects presenting with symptoms on PV stenosis, using the same imaging technique as pre-ablation. Pre-ablation and post-ablation CT/MRAs of symptomatic subjects will be analyzed by a core lab to evaluate the level of PV stenosis.
  - Transtelephonic monitoring (TTM) (1M through 12M)  
Subjects will be provided with a TTM device at the 1M follow-up visit and asked to record and transmit a minimum of 1 transmission (60 seconds) every week through the end of month 5 of follow-up. Starting at month 6 of follow-up, subjects will be asked to record and transmit a minimum of 1 transmission (60 seconds) every month until the effectiveness evaluation period is completed (12 months post index procedure). Subjects will also be asked to transmit any symptom-triggered episode that occurs from the time they receive the TTM device through the 12M follow-up visit. A core lab will be used to evaluate and assess the TTM tracings.
- TTM monitoring will be conducted as follows:
- Distribution and start TTM monitoring by Month 1
  - <6M: Weekly transmission of at least 1 scheduled TTM recording
  - ≥6M: Monthly transmission of at least 1 scheduled TTM recording
  - Conduct and transmit TTM recording whenever symptoms are present
- 24 Hour Holter (6M and 12M)  
Holter monitor will be used at 6M and 12M follow-up visit to monitor the subjects' heart rhythm for 24 hours continuously. Following the 24h Holter, subjects will be

contacted by the site to verify if symptoms are experienced during 24h Holter. A core lab will be utilized to evaluate and assess the 24-hour Holter recordings.

For subjects in the NAE subgroup:

- Cerebral MRI, neurological exam and NIH Stroke Scale assessments will be performed at 1M, 3M, 6M and 12M visit in case observations were noted during previous assessments.
- MoCA and mRS assessments are mandatory at 1M visit. Subjects with findings of micro-emboli/neurologic deficits will undergo additional MoCA/mRS through 12M follow-up

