**Table 8.7 A: Summary of Subject Assessments**

Assessments	Pre-ablation	Pre-discharge	7D (D6-8)	M1 (D23-37)	M3 (D76-104)	M6 (D150-210)	M12 (D315-405)	UNS
Clinic visit	●			●	●	●	●	●
Phone Call			● 					
Patient Informed Consent*/Demographics	●							
Medical/AF history	●							
Cardiac Medication Regimen	●	●	●	●	●	●	●	●
Anti-coagulation Regimen	●	●		●	●	●	●	●
CHA2DS2-Vasc Score	●							
NYHA functional Class Scale	●				●			
Pregnancy Test	● 							
QoL (AFEQT questionnaire)	●				●	●	●	
TTE	● 	●						
LA thrombus detection (TEE/ICE)	● 							
ECG	● 	● 		● 				
Cardiac CT/MRA	● 				● 			
Adverse events	●	●	●	●	●	●	●	●
AFL/AT/AF recurrence and repeat ablation				●	●	●	●	●
Arrhythmia Monitoring 				● 				
24-hour Holter/FUP call						● 	● 	
Cardiovascular hospitalization			●	●	●	●	●	●
Cerebral MRI (NAE subjects only)	● 	● 		● 	● 	● 	● 	● 
Neurological Exam (NAE subjects only)**	● 	● 		● 	● 	● 	● 	● 
NIH Stroke Scale (NAE subjects only)	● 	● 		● 	● 	● 	● 	● 
mRS (NAE subjects only)	● 			●	● 	● 	● 	● 
MoCA (NAE subjects only)	● 			●	● 	● 	● 	● 

1. May be substituted with a clinic visit.
2. In all women of childbearing age and potential. To be completed within 72-hours prior to ablation procedure.
3. To be completed within 60 days prior to ablation procedure
4. To be completed the day before or the day of the study ablation procedure. Imaging modality TEE or ICE.
5. To be collected if completed as standard of care.
6. To be completed within 30 days prior to ablation procedure. CT-MRA to be repeated at 3M FU in case the subjects presents with PV stenosis symptoms.
7. To be completed within 72-hours pre-procedure.
8. To be completed within 48-hours post-procedure.
9. To be undertaken if neurologic symptoms and/or cerebral ischemic lesions identified in a prior evaluation.

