11.5.3 NAE Endpoints

The occurrences of asymptomatic and symptomatic cerebral emboli will be summarized by timepoints of pre- and post-ablation procedure. Frequency, anatomic location, and size (diameter and volume) of cerebral emboli at baseline, post-ablation and during follow-up will also be

Biosense Webster, Inc

summarized. Neurologic deficits observed post ablation and during follow up period will be summarized.

The National Institutes of Health Stroke Scale (NIHSS) scores and Montreal Cognitive Assessment (MoCA) scores at baseline, post ablation and during follow-up will be summarized with descriptive statistics.

These analyses will be performed in the NAE population.

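### SAP 11.5.3 summarises MoCA and NIHSS by visit only; paired change should be added, and own baseline at the later visits, which cover only subjects with earlier findings

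*SAP*

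**What the plan says.** **Analysis.** SAP 11.5.3 gives one line to the two scales, in the NAE population: "Stroke Scale (NIHSS) scores and Montreal Cognitive Assessment (MoCA) scores at baseline, post ablation and during follow-up will be summarized with descriptive statistics". SAP 11.1 defines the statistics for a continuous variable: number with data, mean, SD, median, both quartiles, minimum and maximum, on non-missing values. Change from baseline is not among them. The endpoint lists (Protocol 3.2.2, SAP 6.2.1) ask only for a summary of each score. SAP 11.7, by contrast, plans both baseline values and change from baseline for AFEQT.

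**Schedule.**
- Before ablation, in all NAE subjects, both scales "are required to be performed within 72- hours pre-procedure to evaluate the neurological condition" (Protocol 8.2.1).
- After ablation, Protocol 8.2.4 requires "Neurological Evaluation using the NIH stroke Scale within 48- hours post procedure, prior to discharge".
- For MoCA, Protocol 8.3 states: "MoCA and mRS assessments are mandatory at 1M visit".
- After that, assessment is conditional. For NIHSS: "NIH Stroke Scale assessments will be performed at 1M, 3M, 6M and 12M visit in case observations were noted during previous assessments". For MoCA: "Subjects with findings of micro-emboli/neurologic deficits will undergo additional MoCA/mRS through 12M follow-up". Table 8.7 A, footnote 9, sets the same condition: "To be undertaken if neurologic symptoms and/or cerebral ischemic lesions identified in a prior evaluation".

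**Who enters.** Protocol 4.2, criterion 37, keeps out of the subgroup anyone with an "Unresolved pre-existing neurological deficit".

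**The concern.** Two features of the planned table limit what it can tell a reader.

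1. It compares groups of scores, not subjects. A stable mean and SD at baseline and 1 month are compatible with nobody changing, and equally with several subjects declining while others improve. The paired values exist for every subject assessed at both visits, but the plan does not use them.
2. The later rows contain a different set of people. From 1 month (NIHSS) or 3 months (MoCA), the scheduled score comes only from subjects with an earlier lesion, symptom or deficit, while the baseline row contains everyone. A difference between the rows can come from who was assessed rather than from any change. The n required by SAP 11.1 shows that the group is smaller, but not where that group started.

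No test is planned for these endpoints (SAP 11.5), so the descriptive table is the whole result for two listed secondary safety endpoints.

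**Working it through.** The documents state no power, alpha or precision for NIHSS or MoCA, so there is no plan figure to reproduce. The first step is textual; the rest is illustration.

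**Step 1. Who is measured when** (Protocol 8.2.1, 8.2.4, 8.3, Table 8.7 A)

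| | Baseline | Post-ablation | 1 month | 3, 6, 12 months |
|---|---|---|---|---|
| NIHSS | all NAE | all NAE | earlier findings only | earlier findings only |
| MoCA | all NAE | not scheduled | all NAE | earlier findings only |

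Full-cohort pairs therefore exist for NIHSS (baseline to 48 hours) and MoCA (baseline to 1 month). Every later cell is a selected subset.

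**Step 2. MoCA: what the visit-level statistics hide**

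Inputs: 40 subjects (Protocol 3.1.3). Assumed: a fall is a worsening; the same mean and SD at both visits; SD 1.5 to 3; within-subject correlation r of 0.5 to 0.9; a fall of 2 or more points as an example threshold.

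SD of change = SD × √(2(1 − r)). For whole-number scores, P(fall ≥ 2) = Φ(−1.5 / SD of change). For SD 2 and r = 0.7: 2 × √0.6 = 1.549; Φ(−0.968) = 0.166; × 40 = 6.7 subjects.

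Expected number of 40 falling by 2 or more:

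| | r = 0.5 | r = 0.7 | r = 0.9 |
|---|---|---|---|
| SD 1.5 | 6.3 | 3.9 | 0.5 |
| SD 2 | 9.1 | 6.7 | 1.9 |
| SD 3 | 12.3 | 10.4 | 5.3 |

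Within a row, the visit-level mean and SD are the same throughout. These counts include test-retest variation; they are not estimates of harm.

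A constructed example shows that the whole set of statistics can match:
- Baseline (score × subjects): 23×1, 24×3, 25×10, 26×9, 27×10, 28×3, 29×3, 30×1.
- 1 month: 23×2, 24×2, 25×7, 26×14, 27×8, 28×3, 29×3, 30×1.
- Falls of 4 points: 29→25 twice, 28→24 once, 27→23 once (total −16).
- Rises of 1 point: two from 24, seven from 25, two from 26, three from 27, two from 28 (total +16).

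At both visits the sum is 1050 and the sum of squares 27656. The mean is 1050/40 = 26.25 and the SD √((27656 − 1050²/40)/39) = √(93.5/39) = 1.55. The median is 26, the quartiles 25 and 27, and the range 23 to 30. All eight SAP 11.1 statistics are identical, yet four subjects fell by 4 points.

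**Step 3. Later visits: subset against all-subject baseline**

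Input: 9 of 39 feasibility subjects had new asymptomatic lesions (Protocol 1.2.3), or 23.1%. The exact 95% interval is 11.1% to 39.3%. On 40 subjects this is about 9 (4.5 to 15.7). Applying this rate here is an assumption.

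Suppose nobody changes and the n followed are an average draw from the 40. The difference between their mean and the all-subject baseline mean has SE = SD × √((1/n)(1 − n/40)).
- n = 9: √(0.1111 × 0.775) = 0.2934, so 1.96 × SE = ±0.86 (SD 1.5), ±1.15 (SD 2), ±1.73 (SD 3).
- Extremes: n = 16 with SD 1.5 gives ±0.57; n = 4 with SD 3 gives ±2.79.

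If those 9 truly start d points away from the other 31, a shift of d × 31/40 is added: 0.78 points for d = 1 and 1.55 for d = 2, in either direction. Conversely, a true 1-point decline is fully hidden if they start 1/0.775 = 1.29 points higher. The documents give no basis for the size or sign of d. Against the subjects' own baseline, both artefacts are exactly 0.

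**Step 4. NIHSS: why the gain is small**

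If criterion 37 means that nearly everyone starts at 0 (assumed), a post-ablation mean of 0.05 in 40 subjects is either two subjects at 1 (SD 0.22, maximum 1) or one subject at 2 (SD 0.32, maximum 2). SD and maximum tell the two apart, so the number who worsened can usually be worked out from the planned table.

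**The case against.** The strongest reply is that the SAP delivers the endpoint as written. The endpoint is a summary of scores, SAP 11.5.3 summarises them, and SAP 11.5 makes all secondary endpoints descriptive. That stands: there is no conflict between the documents, and this point proposes a better description rather than correcting a breach.

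A second reply is that individual worsening already has its own endpoint. SAP 6.2.1 lists new or worsening neurologic deficits compared with baseline, SAP 8.1 requires evaluations before and after ablation for it, and a neurologist performs the exams. That also stands, so a reader should not infer that neurological harm would go undetected. Stroke and TIA are counted in the primary composite as well. What remains is at score level: the deficit endpoint is not defined on MoCA or NIHSS scores and gives no change in either.

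Third, the magnitudes rest mostly on assumptions. The SD, correlation, threshold and baseline difference are not in the documents. The 9/39 rate is a loose proxy: two of those nine subjects had interrupted warfarin and one had a noted air embolism, while this trial requires uninterrupted anticoagulation. Symptoms can also trigger follow-up, and Table 8.7 A footnote 10 allows unscheduled assessments. All of this is fair. The figures show what can happen, not what will.

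Fourth, a bare count of worsened subjects could present measurement noise as harm. Step 2 gives 0.5 to 12.3 of 40 with no shift in the mean, and this is a single-arm study. That is right, and the fix carries the condition.

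**Conclusion.** The point holds as a minor, free improvement. The text settles its core: the plan gives visit-level statistics only, and the scheduled later visits cover a selected subset. The size depends on the assumed MoCA SD and correlation and on the feasibility lesion rate. The gap matters mainly for MoCA and is small for NIHSS. It concerns descriptive secondary tables in about 40 subjects; the primary tests, alpha and sample size are untouched.

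Three stronger readings are tempting and are not supported:
- That the later-visit rows are biased in a known direction. Nothing in the documents says that subjects with findings start higher or lower than the others.
- That NIHSS worsening is hidden. With baselines near 0, it can usually be read from the planned statistics (Step 4).
- That the denominator for new lesions is left open because SAP 11.5.3 does not repeat it. SAP 8.1 requires MRI before and after ablation for new lesions, and SAP 11.5 excludes subjects with missing outcomes, so the denominator is already implied.

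**What to change.** In SAP 11.5.3:
1. Summarise paired change from baseline for MoCA at 1 month, and for NIHSS at the post-ablation assessment (small gain), in subjects with both values, in the way SAP 11.7 already does for AFEQT.
2. At the conditional visits (NIHSS from 1 month, MoCA from 3 months), show the assessed subjects' own baseline and their change, with n.
3. If a count of worsened subjects is reported, prespecify the point threshold for each scale, since the documents give none, and note that the count includes test-retest variation in a single-arm study.

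The cost is a few sentences and a few tables from scores already scheduled for collection. No added visits, assessments, subjects or tests are needed.

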11.6 Analysis of Procedural Data

Procedural data such as total procedure duration, fluoroscopy duration and dose, RF application time, balloon dwell time, time to effect (PVI), number and time of RF applications per PV location, fluid delivery, output and balance will be summarized with descriptive statistics. These analyses will be conducted using the PP population and the roll-in subjects.

11.7 Analysis of Atrial Fibrillation Effect on Quality-of-life Questionnaire

AFEQT includes 20 questions on a 7-point Likert scale. Questions 1 - 18 evaluate Health Related Quality of Life (HRQoL) and Questions 19- 20 relate to patients' satisfaction with treatment ^[4].

First 18 questions are also used to calculate Overall AFEQT score and subscale scores across three domains

- Symptoms: Four questions 1 - 4 assess AF related symptoms
- Daily Activities: Eight questions (5 – 12)
- Treatment Concerns: Six questions (13 – 18)

The formula to calculate these scores is as follows:

$$100 - \left[\frac{(\text{sum of severity for all questions answered} - \text{number of questions answered}) \times 100}{\text{total number questions answered} \times 6} \right]$$

Overall and subscale scores range from 0 to 100. A score of 0 corresponds to complete disability, while a score of 100 corresponds to no disability.

Baseline values and changes from baseline at each time point the questionnaire is administered will be summarized descriptively for the following five scores.

- Overall AFEQT Score (18 questions)
- Symptom Subscale Score (4 questions)
- Daily Activities Subscale Score (8 questions)
- Treatment Concern Subscale Score (6 questions)

Biosense Webster, Inc

- Treatment Satisfaction Score (2 questions)

These analyses will be conducted in the PP population and roll-in subjects.

11.8 Analysis of Health Economic Data

The health economic data collected in this study includes the cost and frequency of health care utilization during hospitalization for the study index ablation procedure, as well as any additional hospitalizations during the study period. Because this data does not support the safety and effectiveness of the study catheters and the EPU, it will not be presented in the final report.

12 APPENDIX – ADAPTIVE DESIGN SIMULATION REPORT

Adaptive Design Simulation Report

1. Study Design

This clinical investigation is a prospective, multicenter, single arm clinical evaluation utilizing the Biosense Webster multi-electrode radiofrequency balloon catheter and the Biosense Webster multi-electrode circular diagnostic catheter. The sample size for the study is primarily driven by the safety endpoint. An adaptive Bayesian design¹ will be used to determine the sample size based on the safety endpoint alone. The primary safety and effectiveness endpoints will be evaluated using exact tests for binomial proportions at a one-sided 5% significance level.

The null and alternative hypotheses are for primary effectiveness endpoint are:

Hypothesis $H_0: P_E \leq 0.80$

$H_a: P_E > 0.80$

where P_E is the Proportion of patients with acute procedural success defined as confirmation of entrance block in treated PVs after adenosine and/or isoproterenol challenge. The null and alternative hypotheses for the Primary Safety Endpoint are:

Hypothesis $H_0: P_S \geq 0.15$

$H_a: P_S < 0.15$

where P_S is the rate of Primary Adverse Events

2. Sample Size Justification

The study will utilize an adaptive design. The methods described in Broglio et al.^[1] will be used to determine the sample size based on the safety endpoint alone. Sample size selection interim analyses will be performed when 80, 130, and 180 patients are available for the primary safety endpoint analysis. Predictive probabilities for trial success will be used to determine whether the sample size at the time of the interim analysis will be sufficient or if the trial will continue to the full sample of 230. Power for the effectiveness endpoint assessment is >80% at all sample sizes ≥ 80 subjects.

The final stopping sample size of 230 was determined by power calculations for the primary safety endpoint. Based on a performance goal of 15% for the primary safety endpoint and an anticipated rate of at most 9.5% for the primary safety endpoint, 230 subjects will be sufficient to obtain at least 80% power at a one-sided significance level of 5%.

It is assumed that the attrition rate for the study will be negligible. Study enrollment will continue during each interim analysis until a decision is reached to stop enrollment based on the interim

Biosense Webster, Inc

results. Due to the continued enrollment during this time, we expect an additional 5 to 6 subjects enrolled into the study. These additional subjects will be included in the primary analyses and should account for the potential subject attrition.

3. Adaptive Sample Size Determination

In this section, an incidence of any primary adverse events will be referred to as a failure for the primary safety endpoint. Sample size selection interim analyses will be performed when 80, 130, 180, and 230 evaluable subjects (excluding roll-in) are available for the primary safety endpoint analysis. Safety outcome at 30 days will be used as a proxy for the 3-month primary safety endpoint at each interim. The final safety analysis will be based on complete follow-up for the primary safety endpoint for all evaluable patients. Predictive probabilities of success will be used to determine whether the sample size at each interim analysis will be sufficient or if the trial enrollment will continue. Sample size simulations were performed using performance goals of 15% and 80% respectively for the safety and effectiveness endpoint rates.

At the time of each interim analysis, predictive probabilities of success for safety will be calculated once using the current sample size and again using the maximum sample size allowed. A uniform prior distribution will be assumed for the safety rate at the first interim analysis, and the distribution will be updated with the observed data at each subsequent interim analysis. The number of failures for the primary safety endpoint in subjects with incomplete information will be assumed to follow a beta-binomial distribution. The predicted number of failures for the primary safety endpoint will be estimated from these beta-binomial distributions. The observed and predicted number of failures will provide estimates for the anticipated study outcomes with the sample size at the time of the interim analysis and the maximum sample size allowed. The Bayesian predictive probability of success for safety for each case will be calculated from these estimates. No primary effectiveness endpoint analyses will occur until final sample size selection based on the primary safety endpoint has taken place.

Enrollment will be stopped if the predictive probability of success for safety with the current sample size is greater than 90% or if the predictive probability of success for safety using the maximum sample size allowed is less than 6.5%. Otherwise, enrollment will continue until the 230th subject is recruited. The Statistical Analysis Plan will contain details on all planned analyses. Regardless of whether enrollment stops at one of the interim analyses or continues to a sample size of 230 subjects, the primary analyses of the primary safety and effectiveness endpoints will be conducted after all subjects have completed their 3-month post-procedure evaluation.

4. Power and Type-I Error Simulations

Trial simulations were performed to estimate the Type-I error rate and the power for the success of the safety endpoint under a range of assumptions for the true safety rate and the assumed enrollment schedule. Three different enrollment schedules were considered for the simulations

corresponding to realistic, conservative, and aggressive enrollment schedules based on logistical considerations:

Table 1 Assumed Enrollment Schedules

	Expected number of patients per month													
	M1	M2	M3	M4	M5	M6	M7	M8	M9	M10	M11	M12	M13	M14
Realistic	1.7	3.4	5.1	8.5	11.9	17.0	20.4	23.8	25.5	25.5	25.5	25.5	25.5	25.5
Conservative	1.2	3.0	6.0	10.5	15.0	18.0	21.0	22.5	22.5	22.5	22.5	22.5	22.5	22.5
Aggressive	2.5	5.0	10.0	15.0	22.5	30.0	35.0	37.5	37.5	37.5	37.5	37.5	37.5	37.5

Table 2.a provides the estimated power as a function of the true safety rate under the realistic enrollment schedule based on 10,000 simulations for each scenario. In addition, the table provides the proportion of times we expect to stop enrollment at each interim look either for adequate sample size or for futility. Assuming a true safety rates of 0 to 9.0%, the power for showing success for the safety endpoint is estimated to be greater than or equal to 80.0%. For a safety rate of 9.5% this power decreases to approximately 73.0%. With a true effectiveness of rate of 96.0% and a performance goal of 80.0%, a minimum of 80 patients will provide 99.9% power for meeting the primary effectiveness endpoint. Therefore, the power estimates for the primary safety endpoint closely estimate the overall power of the study.

Since the primary analysis is performed at a 5.0% level Type-I error and the sample size is selected independent of the effectiveness endpoint, the Type-I error for the effectiveness hypothesis is controlled at 5.0%. To estimate the Type-I error for the primary safety endpoint, we considered the hypothetical scenario that the primary safety endpoint is on the decision boundary (highest possible type-I error, i.e. equal to 15%). Based on 25,000 trial simulations, the estimated Type-I error for this scenario was 4.7% (1,175 out of 25,000) with a 95% exact confidence interval of (0.0444, 0.0497). As the primary safety rate moves away from the decision boundary under the null hypothesis (higher than 15%), the Type-I error for the test decreases. Since our study success is defined as meeting both primary safety and effectiveness endpoints and because the Type-I error for each of these tests is controlled at 5.0%, the overall study Type-I error will be controlled at 5.0%.

Table 2.a Estimated power as a function of true safety rate under the realistic enrollment assumption using 10,000 simulations for each scenario

Safety rate	power	N=80	N=130	N=180	N=230
0.050	0.9959	0.4507	0.3913	0.1293	0.0287

Biosense Webster, Inc

0.055	0.9929	0.3838	0.3981	0.1664	0.0517
0.060	0.9868	0.3392	0.3776	0.2003	0.0829
0.065	0.9764	0.2856	0.3610	0.2251	0.1283
0.070	0.9630	0.2571	0.3316	0.2381	0.1732
0.075	0.9384	0.2223	0.2884	0.2437	0.2456
0.080	0.9071	0.2019	0.2678	0.2289	0.3014
0.085	0.8661	0.1881	0.2433	0.2214	0.3472
0.090	0.8005	0.1922	0.2083	0.2079	0.3916
0.095	0.7323	0.1924	0.1873	0.1952	0.4251

Table 2.b Estimated Type-I error on the decision boundary under the realistic enrollment assumption and based on 25,000 simulations

Safety rate	Estimated Type-I Error	95% Confidence Interval
0.15	0.0470	(0.0444, 0.0497)

Table 2.c Provides the proportion of times we would stop the trial at each interim for futility. As the true safety rate increases the likelihood of stopping at the interim analyses for futility also increases, with the highest likelihood being equal to 10.67% for stopping at with 80 patients if the true rate is 9.5%.

Table 2.c Proportion of times the trial will stop at each interim for futility under the realistic enrollment assumption based on 10,000 simulations for each scenario

safety rate	N=80	N=130	N=180
0.050	0.0035	0.0004	0.0001
0.055	0.0058	0.0005	0.0002
0.060	0.0104	0.0011	0.0006
0.065	0.0174	0.0024	0.0013
0.070	0.0257	0.0044	0.0022
0.075	0.0347	0.0089	0.0055

Biosense Webster, Inc

0.080	0.0475	0.0123	0.0095
0.085	0.0604	0.0210	0.0158
0.090	0.0851	0.0311	0.0243
0.095	0.1067	0.0439	0.0354

Tables 3.a, 3.c, 4.a, and 4.c provide the estimated power and futility proportions under the conservative and aggressive scenarios. The estimated type-I error assuming a safety rate of 15% was estimated to be 0.04584 (1,146 out of 25,000) with a 95% exact binomial confidence interval of (0.0432, 0.0485) under the conservative enrollment assumption (Table 3.b), and 0.04208 (1,052 out of 25,000) with a 95% exact confidence interval of (0.0396, 0.0446) under the aggressive enrollment assumption (Table 4.b).

Table 3.a Estimated power as a function of true safety rate under the conservative enrollment assumption using 10,000 simulations for each scenario

Safety rate	power	N=80	N=130	N=180	N=230
0.050	0.9970	0.4641	0.3996	0.1125	0.0238
0.055	0.9926	0.3972	0.4061	0.1525	0.0442
0.060	0.9870	0.3427	0.4105	0.1766	0.0702
0.065	0.9797	0.2993	0.3820	0.2034	0.1153
0.070	0.9634	0.2584	0.3567	0.2180	0.1669
0.075	0.9397	0.2281	0.3228	0.2263	0.2228
0.080	0.9114	0.2098	0.2893	0.2277	0.2732
0.085	0.8662	0.1959	0.2654	0.2145	0.3242
0.090	0.8049	0.1843	0.2208	0.2104	0.3845
0.095	0.7364	0.1917	0.2088	0.1946	0.4049

Table 3.b Estimated Type-I error on the decision boundary under the conservative enrollment assumption and based on 25,000 simulations

Safety rate	Estimated Type-I Error	95% Confidence Interval
-------------	------------------------	-------------------------

Biosense Webster, Inc

0.15	0.04584	(0.0432, 0.0485))
------	---------	-------------------

Table 3.c Proportion of times the trial will stop at each interim for futility under the conservative enrollment assumption based on 10,000 simulations for each scenario

safety rate	N=80	N=130	N=180
0.050	0.0028	0.0002	0.0000
0.055	0.0061	0.0006	0.0002
0.060	0.0093	0.0018	0.0003
0.065	0.0145	0.0021	0.0017
0.070	0.0223	0.0043	0.0035
0.075	0.0350	0.0084	0.0051
0.080	0.0462	0.0116	0.0092
0.085	0.0624	0.0223	0.0142
0.090	0.0775	0.0301	0.0255
0.095	0.1015	0.0395	0.0354

Table 4.a Estimated power as a function of true safety rate under the aggressive enrollment assumption using 10,000 simulations for each scenario

Safety rate	power	N=80	N=130	N=180	N=230
0.050	0.9918	0.3349	0.4029	0.1955	0.0667
0.055	0.9840	0.2836	0.3851	0.2278	0.1035
0.060	0.9793	0.2433	0.3535	0.2561	0.1471
0.065	0.9637	0.2082	0.3215	0.2594	0.2109
0.070	0.9384	0.2008	0.2695	0.2595	0.2702
0.075	0.9098	0.1784	0.2459	0.2498	0.3259
0.080	0.8714	0.1760	0.2112	0.2236	0.3892

Biosense Webster, Inc

0.085	0.8217	0.1705	0.1884	0.2103	0.4308
0.090	0.7721	0.1883	0.1677	0.1887	0.4553
0.095	0.6917	0.1960	0.1562	0.1703	0.4775

Table 4.b Estimated Type-I error on the decision boundary under the aggressive enrollment assumption and based on 25,000 simulations

Safety rate	Estimated Type-I Error	95% Confidence Interval
0.15	0.04208	(0.0396, 0.0446)

Table 4.c Proportion of times the trial will stop at each interim for futility under the aggressive enrollment assumption based on 10,000 simulations for each scenario

safety rate	N=80	N=130	N=180
0.050	0.0071	0.0010	0.0001
0.055	0.0130	0.0023	0.0005
0.060	0.0172	0.0026	0.0006
0.065	0.0270	0.0045	0.0021
0.070	0.0437	0.0093	0.0045
0.075	0.0575	0.0168	0.0069
0.080	0.0756	0.0219	0.0114
0.085	0.0980	0.0291	0.0202
0.090	0.1189	0.0350	0.0267
0.095	0.1434	0.0501	0.0381

Based on the simulation results, we concluded that the study is adequately powered to meet the primary safety and effectiveness endpoints and that the Type-I error for the overall trial success is controlled at 5% for the different enrollment schedules considered.

